To ensure the study generates findings that are generalisable beyond a single NCA, we have chosen to work with two NCAs, MINAP and PICANet. MINAP and PICANet are delivered by different suppliers and involve different clinical specialties working with different patient groups, multiple professional groups (medical and nursing), and include multiple types of measures (structure, process, and outcome). They also differ in data quality and completeness. MINAP has been running continuously since 2000, delivered by the National Institute for Cardiovascular Outcomes Research, and data are contributed by all hospitals in England, Wales and Northern Ireland that admit patients with acute coronary syndromes. PICANet was set up in 2002 by the Universities of Leeds, Leicester and Sheffield and contains data from all NHS Paediatric Intensive Care Units (PICUs) in England and Wales.

There are three main funding arrangements for independent NCAs: subscription by NHS Trusts; funded by a charity or professional body; or funded by NHS England. To explore the impact of funding arrangements, in Phase 1 we will also gather data on the National Cardiac Arrest Audit (NCAA; funded by Trust subscription), the National Audit of Cardiac Rehabilitation (NACR; funded by the British Heart Foundation), and the Elective Surgery National PROMs Programme

(funded by NHS England). There are a number of independent surgery NCAs where participation is at the individual clinician, rather than Trust, level; to understand the impact of this difference, in Phase 1 we will gather data about the British Association of Urological Surgeons (BAUS) audits. In Phase 5, we will explore the applicability of QualDash to those independent NCAs where data is collected intermittently rather than continuously,

We will work with three NHS acute Trusts (sites A-C) that participate in both MINAP and PICANet. These Trusts have been selected to ensure variation in key outcome measures (MINAP: 30 day mortality for ST-elevation myocardial infarction (STEMI) patients; PICANet: risk adjusted standardised mortality ratio), as shown in Table 1.

Because Trusts that participate in PICANet tend to be larger and to be teaching hospitals, they are not representative of the range of Trusts that participate in MINAP. Therefore, MINAP use will also be studied in two district general hospitals (DGHs; sites D-E) that do not have a PICU. These have been selected to ensure variation in the same key MINAP measure.

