Sample: Data will be collected for sites A-E, with two control Trusts per intervention Trust, matched on comparable outcomes pre-intervention. Contextual factors in the QualDash program theory may be used as additional matching criteria. A CITS study requires data for a minimum of three time points pre-intervention and three time points postintervention and must also allow for any seasonal effect on the outcomes. 106 Therefore, monthly data will be obtained for 24 months pre-intervention and 12 months post-intervention. For MINAP, Cumulative Missed Opportunities for Care (CMOC) will be used as the primary process measure (described below). The average CMOC for patients on a ward will be averaged for each month, so that there are 36 observations clustered within each of 15 hospitals. Taking the intra-class correlation to be 0.15, this yields a design effect of 6.25. Hence the effective number of observations is 15*36/6.25=86.4. Using Cohen's approach to sample size calculation this means that an effect size of 0.17 can be estimated with 80% given that there are six parameters in the model (including the coefficient for QualDash). Converting this to the percentage of variation that can be explained by the model, this yields 20.5%. Translating this back to CMOC, currently 49.6% are discharged from hospital without missing any of the nine opportunities for care, and we would be powered at the 80% level to detect an improvement from an average of 8.33 opportunities achieved to 8.46. Thus our study has good power to detect small but meaningful clinical improvements. For PICANet, the primary process measure will be the use of non-invasive ventilation first for patients requiring ventilation, 10% of the admitted population. 107 On average there are 5.25 ventilation cases per month per hospital. With a further design effect from patients clustered within hospitals, based on the reported ICC=0.065 giving DEff=1.276, the actual anticipated number of patients is 1701 giving an effective number of 213: 71 exposed to QualDash and 142 controls. This yields 80% power to detect a change from 32% to 53% which is a feasible target given that the use of non-invasive ventilation first will be highlighted by QualDash.

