Data collection: For MINAP, the primary outcome will be the composite process measure CMOC. This has nine components (pre-hospital ECG, acute use of aspirin, timely perfusion, prescription at hospital discharge of aspirin, thienopyridine inhibitor, ACE-inhibitor, HMG-CoA reductase inhibitor, beta blocker, referral for cardiac rehabilitation) and, in previous work by members of the team, CMOC has been shown to be associated with mortality. ¹⁰⁸ For PICANet, the primary outcome will be use of non-invasive ventilation first for patients requiring ventilation, which has been shown to be associated with reduced mortality. ¹⁰⁷ Secondary outcomes will be determined on the basis of findings from Phase 1 regarding interviewees' perceptions of the value of particular measures and the extent to which they can be impacted by QI initiatives and through consultation with our LAG.

Analysis: Monthly MINAP and PICANet data will be extracted to spreadsheets for analysis with R software. ¹⁰⁹ For each intervention Trust, there will be 72 data points prior to introduction (24 for the intervention Trust and 48 for the control Trusts) and 36 data points post intervention (12 for the intervention Trust and 24 for the control Trusts). For both NCAs, the outcome will be regressed upon time and the intervention (QualDash). The time component will include a seasonal effect (quarterly effect) and will allow for a (linear) time trend. To account for clustering of monthly observations within hospitals a random intercept will be fitted, although a fixed effect for hospital as a sensitivity analysis will be explored. Although the intervention is abrupt, its impact may well be 'phased in' over a few months, perhaps three. The timing of the bedding in of the intervention will be reported from the multi-site case study. Then a partial effect can be considered for this period with the interaction effect stepping up in a linear fashion.

4b. Multi-site case study

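### The primary CITS model as listed names no intervention-group term, so about 17% of any remaining level gap between intervention and control Trusts would be read as QualDash effect

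*Protocol*

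**What the plan says.** Protocol section 4a, Analysis, gives the model for both audits: "the outcome will be regressed upon time and the intervention (QualDash"). On time it adds: "The time component will include a seasonal effect (quarterly effect) and will allow for a (linear) time trend". On clustering: "a random intercept will be fitted, although a fixed effect for hospital as a sensitivity analysis will be explored". No indicator separating intervention from control Trusts is listed. For a phased-in impact, the same paragraph says: "Then a partial effect can be considered for this period with the interaction effect stepping up in a linear fashion".

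Section 4a, Sample, gives the MINAP power inputs: "there are 36 observations clustered within each of 15 hospitals", "Taking the intra-class correlation to be 0.15, this yields a design effect of 6.25", and power of 80% "given that there are six parameters in the model (including the coefficient for QualDash"). There are 24 months before and 12 after the introduction of QualDash. Each intervention Trust has two control Trusts matched on pre-intervention outcomes, giving 5 v 10 hospitals for MINAP and 3 v 6 for PICANet.

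Of the three Trusts that take part in both audits, Setting/context says: "These Trusts have been selected to ensure variation in key outcome measures". The measures used were 30-day STEMI mortality and the PICANet standardised mortality ratio. The two district general hospitals were also chosen for variation in STEMI mortality.

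**The concern.** A controlled interrupted time series earns its credibility from change within hospitals: each intervention hospital is compared with its own past, and controls supply the shared time course. If the only terms are time, QualDash and a random hospital intercept, the fit also uses the comparison of intervention with control hospitals at the same calendar time. A random intercept shrinks hospital levels towards a common mean, so it removes a standing difference between the two groups only in part. The remainder falls on the one coefficient that separates the groups, which is QualDash.

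The intervention Trusts were chosen purposively and not at random, so equal levels on Cumulative Missed Opportunities for Care (CMOC) or on non-invasive ventilation first rest on the matching alone. The bias could run in either direction. The CITS estimate matters beyond Phase 4: it is to be considered when judging whether a cluster trial is justified, and the protocol's summary says it will inform the effect size for that trial.

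**Working it through.** **Inputs.** Section 4a: T = 36 months (24 + 12), so the post-intervention fraction is 1/3; N = 15 hospitals, intervention fraction p = 5/15 = 1/3 (PICANet 3/9, also 1/3); ICC 0.15. Total variance is scaled to 1.

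**The plan's own figures.** Design effect = 1 + 35 × 0.15 = 6.25; effective number = 540/6.25 = 86.4. Both reproduce.

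**Model as listed.** Intercept, linear month, three quarter terms, QualDash (intervention × post) and a random hospital intercept. That is 1 + 1 + 3 + 1 = 6 coefficients.

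**Share of a standing gap that reaches the QualDash coefficient (generalised least squares).**

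- Weight on between-hospital information: λ = (1 − ICC)/(1 − ICC + T × ICC) = 0.85/(0.85 + 5.40) = 0.85/6.25 = 0.136.
- A gap that is constant over time enters only through the between-hospital part: λ × (1/3) × p(1 − p) = 0.136 × (1/3) × (2/9) = 0.01007.
- Within-hospital information on QualDash: (2/9) × p(1 − p) + (2/9) × p² × (1 − R²), where R² is the part of the post indicator explained by trend and quarter. Adjusted for quarter, month has variance 96 + 2/3 = 96.67 and covariance 4 with the post indicator, so R² = 16/(96.67 × 2/9) = 0.745. This gives 0.04938 + 0.02469 × 0.255 = 0.05568.
- Between-hospital information: λ × (1/9) × p(1 − p) = 0.136 × (1/9) × (2/9) = 0.00336.
- Share = 0.01007/(0.05568 + 0.00336) = **0.171**.

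Numerical fitting of the full design gives the same 0.1706, for 5 v 10 and for 3 v 6 hospitals alike.

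| Model (ICC 0.15, MINAP) | Share of gap read as effect | SE (total-SD units) |
|---|---|---|
| As listed, random intercept | 17.1% | √(0.85/(540 × 0.05904)) = 0.163 |
| As listed plus a common post-period term | 19.1% | 0.173 |
| Random intercept plus intervention-group term | 0 | √(0.85/(540 × 0.05568)) = 0.168 |
| Hospital fixed effects | 0 | 0.168 |

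SE ratio: 0.1681/0.1633 = 1.03.

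**Other ICC values.** The share is 40% at 0.05, 24% at 0.10, 8% at 0.30 and 4% at 0.50. The protocol's figure is 0.15; the rest show sensitivity only. PICANet's effective number also rests on the 6.25: 5.25 × 36 × 9 = 1701, and 1701/(6.25 × 1.276) = 213.

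**Estimated variances.** An unmodelled gap inflates the estimated intercept variance, which raises the weight on within-hospital change. In a small REML simulation (150 runs per setting), the difference between the models without and with a group term was about 14% of a 0.5 SD gap and 8% of a 1 SD gap.

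**Size on the CMOC scale.** The protocol gives no standing gap, so these are assumptions, at a share of 0.171 and against the detectable improvement of 8.46 − 8.33 = 0.13:

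| Assumed gap | Added to QualDash estimate | Fraction of 0.13 |
|---|---|---|
| 0.05 | 0.009 | 7% |
| 0.13 | 0.022 | 17% |
| 0.25 | 0.043 | 33% |

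**Effect on error rate** (known variances, nominal two-sided 5%): a gap of 0.25 total SD gives 0.26 SE of bias and an error rate of about 5.8%; 0.5 SD gives 0.52 SE and about 8.2%.

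**Does the parameter count settle the model?** With n = 86.4, effect size 0.17 and alpha 0.05 (assumed, as it is not stated), power is 79.9% with six predictors besides the intercept and 83.0% with five. The terms listed make five besides the intercept.

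**The case against.** The strongest reply is that the model may already contain the term. The protocol calls the QualDash effect an interaction, which normally implies main effects, and the stated 80% power fits six predictors besides the intercept better than five. Trend, three quarters, QualDash and a group indicator would make six. That stands as a reason for doubt. It does not prove the point, because the sixth predictor could equally be a common post-period term, and with that term the share is 19.1%.

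A reader might infer that a random intercept is the wrong choice and that fixed effects are the only cure. The calculation does not support this: keeping the random intercept and adding a group term gives zero leakage and the same SE. A reader might also infer that purposive site selection creates the gap. It does not do so by itself, since controls are matched to whichever Trusts were chosen, and selection for variation means spread, not a shift in one direction. Matching on pre-intervention outcomes is aimed at exactly this threat. The protocol gives no tolerance, however, and does not say outright that the matching variable is CMOC or non-invasive ventilation first.

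Finally, the fixed-effect analysis is planned and would expose a discrepancy, and the CITS result is not a formal progression criterion. Both are true. But nothing says which result prevails if the two models differ.

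**Conclusion.** The point holds in a limited form. The primary model, fitted as listed, passes about 17% of any residual level gap into the QualDash estimate at ICC 0.15, and less when variances are estimated and the gap is large. The cause is the unlisted intervention-group term.

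The result assumes that the listed terms are the whole model, equal residual variance and no serial correlation. For PICANet's binary outcome it also assumes a linear approximation. The practical size depends on a gap for which the documents give no figure. With close matching on the process measure the bias is small; at the assumed gaps above it is a distortion at the margin. It would be wrong to conclude that the CITS estimate is materially biased or that the design is invalid. Importance is minor to moderate: the estimate is non-randomised, the between-Trust contrast has no place in it, and removing it is easy.

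**What to change.** In section 4a, Analysis, state one of the following for both audits:

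- the primary model keeps the random hospital intercept and includes a main effect for intervention versus control Trust, constant over time, alongside the trend, quarter and QualDash terms; or
- the hospital fixed-effect model is primary, and the random-intercept model is the sensitivity analysis.

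In the same edit, list the terms that make up the six parameters in the sample-size paragraph, so that model and power calculation agree, and name the measure on which controls are matched.

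The cost is a sentence or two of text and, at ICC 0.15, a MINAP standard error about 3% larger (0.163 to 0.168 in total-SD units). No extra data are needed, and the fixed-effect analysis is already planned.

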In the multi-site case study, data will be collected through ethnographic observation and interviews. Ethnography is the study of people in their environments where the researcher participates in the setting in order to collect data.⁹⁹ Ethnographic methods, such as non-participant observation, have been used in previous realist evaluations as part of the process of theory testing and refinement,^{69,100} and such methods have been argued as essential for studying both the implementation of QI interventions²⁹ and the introduction of technology in healthcare.¹⁰¹ We will follow the Biography of Artefacts (BoA) approach,⁵⁹ which has been used successfully in a number of studies of HIT^{58,102} and which we have found useful in our current study of dashboards. This approach involves 'strategic ethnography',⁵⁹ studying longitudinally, across different locations, and at different levels of the organisation how practices surrounding a new technology evolve and how previous practices enable and constrain this process.⁵⁸

Interviews are an important complement to ethnographic observation, providing an opportunity for the researcher to ask questions about aspects of practice that might not be immediately intelligible to an observer, as well as for gaining interviewees' reasoning about QualDash. Logfiles will provide additional data on when and how QualDash is used.

A&F interventions, and QI interventions more generally, require longitudinal evaluation to allow sufficient time for staff to implement changes and incorporate them into their practice. Similarly, the evaluation of HIT should allow time for staff to integrate the technology into their practices and evolve those practices to take advantage of the functionality offered by the technology. Therefore, data will be collected over a 12 month period.

Team

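### The 80% power figures for both audits make no allowance for the gradual onset that the analysis section says is likely; under a three-month phase-in, power for the stated full effects would be lower

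*Protocol*

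**What the plan says.** Protocol section 4a, Sample, plans 24 monthly points before launch and 12 after, with two control Trusts per intervention Trust. For MINAP it concludes "we would be powered at the 80% level to detect an improvement from an average of 8.33 opportunities achieved to 8.46". For PICANet it concludes "This yields 80% power to detect a change from 32% to 53% which is a feasible target". Neither calculation mentions onset.

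Section 4a, Analysis, describes the model for the same data: "Although the intervention is abrupt, its impact may well be 'phased in' over a few months, perhaps three". It adds that the timing will be reported from the multi-site case study, and that a partial effect rising linearly over that period is an option. The wording leaves it as something to consider, not as a fixed part of the model.

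The Phase 4 Summary of method takes the same view of onset. It says that audit-and-feedback and quality improvement interventions "require longitudinal evaluation to allow sufficient time for staff to implement changes and incorporate them into their practice".

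**The concern.** The sample size and the analysis plan describe different exposure patterns for the same 12 months. Three of 12 post-launch months is a quarter of the exposed time. If those months carry only part of the effect, one of two things happens. A ramp term has less variance than a step, so its coefficient is estimated less precisely. A step term estimates a diluted average. Either way, 80% is not the power for the full effect.

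What is at stake is how a null or imprecise result would be read. The Sample paragraph concludes that power is good for small improvements. Phase 5 takes the CITS impact into account, outside the formal progression criteria, when judging whether a cluster trial is justified. The Summary says CITS results will set the effect size for that trial. The protocol also leaves open whether 8.46 and 53% are plateau levels or averages over the year, and under the ramps below these differ by about 8–17% of the effect.

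**Working it through.** **Reproducing the stated figures** (alpha is not stated; two-sided 5% assumed)

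- MINAP: "Hence the effective number of observations is 15*36/6.25=86.4", with design effect 1 + 35 × 0.15 = 6.25. For f² = 0.17, six parameters and λ = 0.17 × 86.4 = 14.7, the noncentral F test on 6 and 79.4 degrees of freedom gives 79.9%. This is an omnibus test of all six parameters.
- PICANet: 9 hospitals × 36 months × 5.25 cases = 1701; 1701/6.25/1.276 = 213; one third is 71 and two thirds is 142. For 32% against 53%, power is 80.3% with continuity correction and 84.2% without.

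Both 80% figures reproduce, and neither contains an onset term.

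**Phase-in loss for a single QualDash coefficient**

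Take a nominal 80%, so that the expected z is 1.960 + 0.842 = 2.802. Let x be the exposure in an intervention hospital: 0 for 24 months, the ramp for three months, then 1 for nine.

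- Ramp fitted: power = Φ(2.802 × √(SS_ramp/SS_step) − 1.960), where SS = Σx² − (Σx)²/36 after removing the hospital intercept.
- Step fitted: power = Φ(2.802 × a − 1.960), where a is the mean post-launch effect as a fraction of the full effect.

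For a ramp of 1/4, 1/2, 3/4:

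- SS_step = 12 − 144/36 = 8.
- SS_ramp = 9.875 − 110.25/36 = 6.81, and √(6.81/8) = 0.923. Power = Φ(0.625) = 73.4%.
- a = 10.5/12 = 0.875. Power = Φ(0.491) = 68.8%.

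| Ramp in months 1–3 (assumed) | a | SS_ramp | Power, ramp fitted | Power, step fitted |
|---|---|---|---|---|
| 1/3, 2/3, 1 | 0.917 | 7.19 | 75.7% | 72.8% |
| 1/4, 1/2, 3/4 | 0.875 | 6.81 | 73.4% | 68.8% |
| 0, 1/3, 2/3 | 0.833 | 6.78 | 73.2% | 64.6% |

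Repeating this with 5 + 10 and 3 + 6 hospitals, with fixed intercepts or a random intercept at ICC 0.15, and with no time terms, linear trend plus quarters, or month effects, gives 73–76% for the ramp and 64–73% for the step. Adding a common post-launch term and an intervention-group term to the random-intercept model with trend and quarters gives 75–77% for the ramp. No three-month ramp tried keeps 80%.

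**In detectable-effect terms**

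The full effect needed for unchanged power is about 5–9% larger with the ramp fitted (the range of standard-error ratios) and about 9–20% larger with a step (1/0.917 to 1/0.833). Scaling the stated changes directly, 0.13 CMOC opportunities becomes about 0.14 (ramp) or 0.14–0.16 (step). Likewise 21 percentage points becomes about 22–23 or 23–25.

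**The case against.** A reader might infer that the plan assumes a full effect in every post-launch month while expecting a phase-in, so that true power is 69–73%. The documents do not support that, for four reasons.

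- **Strength of the text.** The protocol says phase-in may well happen, over perhaps three months. It does not say that it will, and it gives no ramp shape.
- **What the calculations model.** Neither is a test of a post-launch step. MINAP's is an omnibus test, so only QualDash's share of f² would be diluted, and that share is not given. Scaling it by factors of 0.875 to 0.923 gives 66–72% if QualDash has the whole share, 74–76% at half and 77–78% at a quarter. PICANet counts "the actual anticipated number of patients is 1701 giving an effective number of 213: 71 exposed to QualDash and 142 controls". The 71 are one third of all 36 months and so include pre-launch patients. Only about 71/3 = 24 are post-launch, and a crude comparison of 24 with 47 has about 40% power.
- **Which analysis.** A loss to 69% needs a plain step. The ramp that the Analysis paragraph describes loses less.
- **Which effect.** If 8.46 and 53% are 12-month averages, a step analysis loses nothing.

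All four stand, and they rule out any single replacement figure. It is also fair that the loss is modest. For PICANet, dropping the continuity correction moves base power by about four points, which is comparable to the loss with the ramp fitted.

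They do not remove the point. The two paragraphs still describe different exposure, and correcting the PICANet count would leave onset unaddressed. Nor is this something left for an SAP: the protocol itself states the power, the expected effect and the likely onset.

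**Conclusion.** The point holds as a conditional one. The 80% statements ignore an onset pattern that the same section calls likely. Under a three-month linear phase-in, with the stated effects taken as full effects after bedding-in, a nominal 80% becomes about 73–76% with the ramp fitted and about 64–73% with a plain step. These figures rest on two-sided 5%, assumed ramp shapes, and 80% being the right base for the QualDash coefficient, which the protocol does not show. The relative loss is therefore better supported than any absolute power. It is a moderate understatement of the detectable effect. It is not an arithmetic error in the stated figures, which reproduce, and for PICANet it is smaller than the problem of counting pre-launch patients as exposed.

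**What to change.** In the Sample paragraph of section 4a:

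1. Recompute power, or the detectable effect at 80%, for the QualDash coefficient in the planned model. Code exposure as 0 before launch, a linear ramp over the assumed phase-in, then 1.
2. State the ramp and its length as assumptions, and restate the 80% figures or the detectable effects to match.
3. Say whether 8.33 to 8.46 and 32% to 53% refer to the level after bedding-in or to the 12-month average.

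Do not just replace 80% with about 73%. That would keep a base which, for MINAP, comes from a six-parameter omnibus test and, for PICANet, from a count that includes pre-launch months.

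The cost is a recalculation, revised wording and a less favourable stated figure. No extra data or sites are needed.
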